### 7.3.2 Secondary efficacy analysis

#### 7.3.2.1 Week 22 treatment effect

As mentioned in Section 3, the Week 22 treatment effect of LCI699 has already been reported in a CSR.

Similar analyses to those performed for the Week 22 treatment effect will be performed for scheduled assessment time points during the extension periods of the study.

A patient is considered to be a responder at a particular time point if the mean UFC level (at least two 24-hour measurements) at that time point is  $\leq$  ULN or represents a  $\geq$  50% decrease from baseline. Patients who discontinue for a disease or treatment related reason (e.g. death, adverse event, clinical disease progression etc.), or whose mean UFC levels are higher than the normal limit and experience  $<$  50% decrease in UFC are classified as non-responders or uncontrolled. If mUFC is missing at a particular time point, then the value will not be imputed but the patient will be considered a non-responder at that time point.

The denominator for the response rate calculation is the number of patients in the safety analysis set for weeks 10 and 22, which is the core phase. For time points after the core phase, the denominator will exclude patients who did not enter the extension phase. Patients who discontinued due to administrative reasons will also not be included in the denominator of any time points after the time of their discontinuation. In addition, patients who are ongoing without reaching the analysis time point will also be excluded. Early discontinued patients (including those discontinuing in the core phase) will be considered as non-responders for all time points after discontinuation.

As a supportive analysis, the response rate will be calculated using only the number of observed mUFC samples at each time point. Patients who have discontinued prior to the assessment time

point, or who are ongoing but do not have a valid mUFC value, will not be counted in the denominator.

The proportion of responders and the associated two-sided 95% confidence interval will be estimated using the exact method.

In addition, responders will be classified further into controlled and partially controlled. Controlled UFC responder is defined as the patient whose mean UFC  $\leq 1.0 \times$  ULN. Partially controlled UFC responder is defined as the patient whose mean UFC  $> 1.0 \times$  ULN but declined by at least 50% from baseline. The proportion of patients with controlled or partially controlled will be provided.

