Drug administration record - LCI699	D	x	x	x	x	x	x	x	x			
Body weight	D		x	x	x	x	x	x	x	x	x	x
Body temperature	D									x	x	
Blood pressure/Pulse rate ¹	D		x	x	x	x	x	x	x	x	x	x
12 Lead safety ECG assessment	D	x			x			x	x	x	x	x
Pituitary MRI	D							x ⁵		x		
Hematology, Blood chemistry, Urinalysis	D		x	x	x	x	x	x	x	x	x	x
IGF-1, TSH, free T4, LH, FSH	D		x	x	x	x	x	x	x	x	x	x
HbA1C	D				x		x	x	x	x		
Testosterone/estradiol	D		x	x	x	x	x	x	x	x	x	x
Urinary Free Cortisol and urine creatinine ³	D		x	x	x	x	x	x	x	x	x	x
Plasma ACTH, cortisol, 11-deoxycortisol and renin	D		x	x	x	x	x	x	x	x	x	x
Plasma and urine aldosterone	D		x	x	x	x	x	x	x	x	x	x
Urine sodium/potassium	D		x	x	x	x	x	x	x	x	x	x
Salivary Cortisol and aldosterone ²	D		x	x	x	x	x	x	x	x	x	x
Plasma and urine Deoxycorticosterone	D		x	x	x	x	x	x	x	x	x	x
Insulin	D		x	x	x	x	x	x	x	x	x	x
Adverse Events	D	As required										

[figure not shown]

	Category	LONG TERM EXTENSION-1								EOT EXTENSION-1	EOS 28 days post last dose ⁶
Visit Number		V12	V13	V14	V15	V16	V17	V18	V19	V777	V778
Days		D154	D182	D210	D238	D266	D294	D322	D406	D490	
Weeks		22	26	30	34	38	42	46	58	70	
Concomitant meds/Therapies	D	As required									
Comments	D	As required									
EOT Extension -1	D	x									
Study completion information	D										x
Visit assessments window is ± 2 days. 1= Blood pressure to be measure in seated position after 3 mins resting. 2= To be collected every 28 days until D322 and then every 3 months at D406 and D490 in the morning and evening. See Section 6.5.5 . 3= Two 24-hour urine collections should be taken prior to visit day, 24-hr urine collections. 4= Pregnancy test at EOS to be serum. 5= Macroadenoma patients only. 6 = This visit is only for patients that have completed long term extension-1 and are not entering long term extension-2.											

[figure not shown]
	Category	LONG TERM EXTENSION-2 ^x			EOT EXTENSION-2 ⁶	EOS 28 days post last dose ⁷
Visit Number		20	21-26	27,28,29...	V777	V778
Months^x		16	Every 3 months	Every 6 months		
Physical examination	S		x	x	x	X
Pregnancy test ⁴	D		x	x	x	X
Drug administration record - LCI699	D	X	x	x		
Body weight	D		x	x	x	X

	Category	LONG TERM EXTENSION-2 ^x			EOT EXTENSION-2 ⁶	EOS 28 days post last dose ⁷
Visit Number		20	21-26	27,28,29...	V777	V778
Months ^x		16	Every 3 months	Every 6 months		
Body temperature	D		x	x	x	X
Blood pressure/Pulse rate ¹	D		x	x	x	X
12 Lead safety ECG assessment	D		x	x	x	X
Pituitary MRI ⁵	D		X ⁵	X ⁵	x	
Hematology, Blood chemistry, Urinalysis	D		x	x	x	X

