## 5 Data Cutoff for Analyses

The data cutoff for the Final CSR will be the date on which the last patient either completes extension-2, or discontinues from the study.

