#### 7.1.2 Patient Disposition

Patient disposition will be summarized separately using the FAS. Counts of the following items will be included in disposition summaries..

- Patients enrolled:
  - Not treated
  - Treated
- Patients treated
  - Discontinued
- Primary reason for end of treatment in the core phase (prior to Week 22)
- Patients completed core phase
  - Patients did not enter extension phase
  - Entered extension phase
    - Completed extension phase
    - Discontinued in extension, with reasons for discontinuation

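### Extension response rates (SAP 7.3.2.1): two rules overlap for core-phase discontinuers, and the missing-value default would count planned completers as non-responders

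*SAP*

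**What the plan says.** SAP Section 7.3.2.1 governs the proportion of responders at scheduled extension visits. Weeks 10 and 22 use the whole safety analysis set. For later visits the rules are:

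- Non-entrants: "For time points after the core phase, the denominator will exclude patients who did not enter the extension phase".
- Administrative exits: "Patients who discontinued due to administrative reasons will also not be included in the denominator" for visits after they leave. The term is not defined.
- Ongoing patients: "In addition, patients who are ongoing without reaching the analysis time point will also be excluded".
- Early discontinuers: "Early discontinued patients (including those discontinuing in the core phase) will be considered as non-responders for all time points after discontinuation".
- Missing values, judged visit by visit: "If mUFC is missing at a particular time point, then the value will not be imputed but the patient will be considered a non-responder".

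A supportive analysis uses only patients with an observed mean UFC at each visit.

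Three other places matter:

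- SAP 7.1.2 lists "Patients did not enter extension phase" as a sub-item of core completers. It also lists completing the extension separately from discontinuing in it.
- SAP Section 5 states: "The data cutoff for the Final CSR will be the date on which the last patient either completes extension-2, or discontinues from the study".
- The Protocol provides two planned exits. One is after Extension-1: footnote 6 to that assessment schedule says of the end-of-study visit, "This visit is only for patients that have completed long term extension-1 and are not entering long term extension-2". The other is from Extension-2, when a roll-over study opens at the site or by 31 December 2019 at the latest (Protocol 3.1 and 5.5.15).

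**The concern.** There are two separate problems.

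First, a patient who stopped in the core phase never entered the extension. One rule takes that patient out of the denominator and another keeps the patient in as a failure. A programmer could defend coding either, and the choice affects every extension visit.

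Second, the ongoing exclusion is empty at the final cutoff, because the SAP waits until the last patient has completed Extension-2 or discontinued. A patient who leaves by a planned route is then not ongoing and, on the SAP's own disposition categories, not a discontinuer. The rule that remains is that a missing mean UFC means non-response. Taken literally, someone who moves to the roll-over study while fully controlled becomes a non-responder at each later tabulated visit for which no value can be mapped.

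SAP Section 3 makes long-term safety and efficacy the focus of the Final CSR. A late fall in the response rate that only reflects planned completion could be misread as loss of effect.

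**Working it through.** **Check of the interval method.** SAP 8.7 specifies Clopper-Pearson: the lower limit is the 2.5% quantile of Beta(x, n − x + 1) and the upper limit is the 97.5% quantile of Beta(x + 1, n − x). For 12/15 this gives 80.0% (51.9 to 95.7), against 80 (52, 96) in SAP Table 4-1. Of the 58 cells in that table, 57 reproduce. The exception, 2 responders of 14 (lower limit printed 0.2, computed 1.8), has no bearing here. The disputed rules carry no figure of their own.

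**Inputs, from the dated status notes in the Protocol's amendment rationales**

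- Amendment 6 (01 March 2014): 19 enrolled, 17 completed the core phase, 2 discontinued, 16 of the 17 entered Extension-1.
- Amendment 5 (01 April 2013): one withdrawal for an adverse event. If this is one of the 2, at most one core exit was administrative.
- Amendment 7 (30 November 2015): 12 ongoing.
- Amendment 9 (03 May 2018): 10 ongoing.
- Responder counts at extension visits are not given and are assumed below.

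**Part 1: core-phase discontinuers, early extension visits, cohorts pooled**

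- Literal non-entrant exclusion: 16.
- Discontinuers kept: 16 + 2 = 18, or 17 if one exit was administrative.
- The one core completer who did not enter (17 − 16 = 1) is out on every reading.

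For r responders the gap is r/16 − r/18 = r/144.

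| r (assumed) | r/16 | r/18 | Gap (points) |
|---|---|---|---|
| 8 | 50.0% | 44.4% | 5.6 |
| 10 | 62.5% | 55.6% | 6.9 |
| 12 | 75.0% | 66.7% | 8.3 |
| 14 | 87.5% | 77.8% | 9.7 |
| 16 | 100% | 88.9% | 11.1 |

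With exact 95% intervals at r = 14: 14/16 = 87.5% (61.7 to 98.4), 14/17 = 82.4% (56.6 to 96.2), 14/18 = 77.8% (52.4 to 93.6).

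**Part 2a: Extension-1 completers who did not enter Extension-2**

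Day 154 by 01 March 2014 puts Day 1 at 29 September 2013 or earlier (153 days before), and Day 490 at 31 January 2015 or earlier (489 days after that). So by 30 November 2015 every remaining entrant was past the end of Extension-1. Of 16 entrants, 12 were still in, so 16 − 12 = 4 had left. Between 0 and 4 of them completed Extension-1 and stopped there.

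The first Extension-2 visit with UFC is Month 19. Assume that the 12 are present and all respond, that the starting denominator is 18, and that m of the 4 leave the denominator as planned completers. The rate is 12/(18 − m).

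| m | Rate | Against the literal reading |
|---|---|---|
| 0 | 12/18 = 66.7% (41.0 to 86.7) | none |
| 1 | 12/17 = 70.6% | +3.9 points |
| 2 | 12/16 = 75.0% | +8.3 |
| 3 | 12/15 = 80.0% | +13.3 |
| 4 | 12/14 = 85.7% (57.2 to 98.2) | +19.0 |

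**Part 2b: Extension-2 completers by roll-over or closure**

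Up to the 10 patients ongoing in May 2018 could be affected. SAP 8.3 maps an end-of-treatment visit to the next scheduled visit if it falls within a window. For six-monthly visits the window runs from 6/2 = 3 to 6 + 6/2 = 9 months after the last scheduled visit. A completer can therefore supply one further value, but nothing after it. Roll-over dates are site-specific and not given, so the effect at any one visit cannot be derived.

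**The case against.** **On Part 1**, the overlap has a sensible resolution. The early-discontinuer sentence names core-phase exits expressly, and SAP 7.1.2 uses non-entry only for core completers. Read that way, both sentences have work to do and the denominator is 18 or 17. A denominator of 16 would empty the parenthesis of effect after the core phase. This stands. A reader might infer an irreconcilable conflict, and the text does not support that. What remains is that no precedence is written, and that the literal alternative errs in the favourable direction.

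**On Part 2**, a reader might infer that the SAP has no rule at all for completers. That is also too strong: the missing-value default covers them. Other readings are open too. SAP Table 8-2 names two extension phases, so the non-entrant exclusion could be applied afresh at Extension-2. Closure could count as administrative. Roll-over patients stay on drug, so one might call them ongoing. The SAP adopts none of these, and its disposition list treats completers as their own category.

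**On harm**, the escape analysis (SAP 7.3.2.4) censors patients without escape at their last visit with a mean UFC, so completers are not failures there. The observed-only analysis, shown alongside, would expose an artificial fall. Both points stand, although the observed-only rate also drops treatment-related dropouts and so cannot replace the intended rate.

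**On the remedy**, removing every Extension-1 completer who did not continue would be wrong. Under Protocol 3.1, entry to Extension-2 depends on the investigator's judgement and on not meeting discontinuation criteria, so some may have stopped for poor response or safety. Removing them would inflate later rates. This stands and shapes the fix.

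**Conclusion.** The point holds as a minor one. In Part 1 the wording permits a pooled denominator of 16 where 18 (or 17) is the likely intent, worth 5.6 to 11.1 points over an assumed 8 to 16 responders. In Part 2 a stated rule, read literally at the final cutoff, gives a wrong result for patients who finish Extension-2 as planned, and possibly for 0 to 4 Extension-1 completers.

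The size of Part 2 is only bounded. A reader might take the 19-point figure at Month 19 as the expected distortion. It needs all 4 leavers to be planned completers and all 12 others to respond, and the documents show neither. If none of the 4 was a planned completer, the Extension-1 effect is nil. For roll-over and closure, only the ceiling of 10 patients is known.

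No test depends on these secondary descriptive rates. The Week 10 primary analysis and the Week 22 results have already been reported and are unaffected.

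**What to change.** In SAP 7.3.2.1:

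1. State that the non-entrant exclusion applies to core completers only. Patients who discontinued in the core phase for non-administrative reasons stay in the denominator as non-responders.
2. State that patients who completed Extension-2 through roll-over or study closure leave the denominator after their last mapped visit under Section 8.3.
3. State that Extension-1 completers who did not enter Extension-2 leave the denominator only if the recorded reason is unrelated to disease or treatment. Otherwise they stay as non-responders.
4. Define *administrative reasons* consistently with items 1 to 3.

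The cost is a few sentences and minor reprogramming of one table. There are two downsides. Early extension rates will be less favourable than with a denominator of 16. The reason for not entering Extension-2 must also be used, and SAP 7.1.2 currently asks for reasons only for discontinuation, not for non-entry.

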### 7.3.2.2 Treatment effect on steroid hormones of HPA-axis

Descriptive statistics will be generated for the change from the respective baselines to different time points in mUFC, plasma adrenocorticotrophic hormone (ACTH), serum cortisol, and steroid hormones, plasma 11-deoxycortisol, 11-deoxycorticosterone, salivary cortisol and aldosterone (morning and evening), urine creatinine, plasma and urine sodium, plasma and urine potassium, plasma renin, testosterone, estradiol, insulin, LH, FSH, IGF-1, free T4, TSH, two-sided 95% CIs using exact method will be provided for the changes from baseline.

### 7.3.2.3 Treatment effect on metabolic abnormalities

The treatment effect on improving the metabolic abnormalities including hypertension, dyslipidaemia, obesity, insulin sensitivity, HbA1c and FPG will be assessed by descriptive statistics on the change from baseline in systolic blood pressure (SBP), diastolic blood pressure (DBP), weight, body mass index (BMI), lipids which includes total cholesterol, triglycerides, HDL-cholesterol, and LDL-cholesterol, QUICKI, HbA1C, and FPG over time, as well as their two-sided 95% CIs using exact method, where QUICKI is the quantitative insulin sensitivity check index derived using the inverse of the sum of logarithms (base 10) of the fasting insulin and fasting glucose as in the following formula:

$$1/(\log(\text{fasting insulin } \mu\text{U/mL}) + \log(\text{fasting glucose mg/dL}))$$

In addition, a listing of relevant concomitant medication(s), with total daily doses and the corresponding cardiovascular/metabolic variable (blood pressure, fasting glucose, HbA1c, fasting lipid profile) lab over time as well as figures and statistical modeling may be provided as an exploratory analysis.

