Stage	A major subdivision of the study timeline; begins and ends with major study milestones such as enrollment, randomization, completion of treatment, etc.
Stop study participation	Point/time at which the patient came in for a final evaluation visit or when study drug was discontinued whichever is later.
Study drug	Any drug administered to the patient as part of the required study procedures; includes investigational drug and any control drugs.
Study drug discontinuation	Point/time when patient permanently stops taking study drug for any reason;
Subject	An individual who has consented to participate in this study. The term Subject may be used to describe either a healthy volunteer or a patient.
Variable	Information used in the data analysis; derived directly or indirectly from data collected using specified assessments at specified timepoints.
Withdrawal of Consent	Withdrawal of consent occurs only when a patient does not want to participate in the study any longer, and does not want any further visits or assessments, and does not want any further study related contact

Amendment 9 (03-May-2018)

Amendment Rationale

Of the 19 patients initially enrolled under Amendment 4, 10 patients are still ongoing as of 03 May 2018.

The purpose of this amendment is to extend the study end date from 31 December 2018 to 31 December 2019 to allow continued access to the study drug for those patients benefitting from the treatment until a separate long-term safety follow-up study (roll-over study) is set up at participating sites.

Additional updates were made to the Protocol glossary and withdrawal of informed consent section to align with the new Personal Data and Withdrawal of Consent language requirement.

Due to the extension of the study duration, this amendment is classified as substantial.

Changes to the protocol and the ICF

[figure not shown]
- Protocol synopsis and Sections 3.1, 5.5.15, and 6: Long Term Extension-2 end day changed from 31 December 2018 to 31 December 2019
- Glossary: Updated Personal Data and Withdrawal of Consent language
- Section 5.5.12 Updated Withdrawal of Consent language
- Updates to the ICF include updating the study end date from 31 December 2018 to 31 December 2019 throughout the document and the implementation of General Data Protection Regulation (“GDPR”) language for sites in the European Union.

IRB/IEC

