5.5.11 Discontinuation of study treatment

Patients may voluntarily discontinue from the study treatment for any reason at any time. If a patient decides to discontinue from the study treatment, the investigator should make a reasonable effort (e.g. telephone, email, letter) to determine the primary reason for this decision and record this information in the patient's chart and on the appropriate CRF pages. They may be considered withdrawn if they state an intention to withdraw, fail to return for visits, or become lost to follow-up for any other reason.

The investigator should discontinue study treatment for a given patient if he/she believes that continuation would be detrimental to the patient's well-being.

Study treatment must be discontinued under the following circumstances and according to Investigator discretion:

- Withdrawal of informed consent.
- Emergence of the following adverse events (compound specific):
 - hypertension defined as office mean sitting systolic BP > 180 mmHg or mean sitting diastolic BP > 110 mmHg (confirmed and persistent*).
- Any of the following laboratory abnormalities:
 - hyperkalemia (serum potassium > 5.5 mmol/L; confirmed and persistent*).
 - hypokalemia (serum potassium < 3.5 mmol/L; confirmed and persistent*).
 - hyponatremia (serum sodium < 130 mmol/L; confirmed and persistent*).
- QTcF > 500 msec, if confirmed by a cardiologist (see [Section 6.6.5](#)).
- QTcF > 480 msec, if the investigator determines it is no longer safe for the patient to continue in the study, based on ECGs, cardiac examination, and recommendation from a cardiologist (see [Section 6.6.5](#)).
- Pregnancy.
- Use of any other therapy for Cushing's disease.
- Any other protocol deviation that results in a significant risk to the patient's safety.

* Persistent is defined as unresolved with LCI699 dose or other concomitant medication changes

Patients who discontinue study treatment should NOT be considered withdrawn from the study. They should return for the assessments indicated in [Section 6](#). If they fail to return to return for these assessments for unknown reasons, reasonable effort (e.g. telephone, email, letter) should be made to contact them as specified in [Section 5.5.13](#).

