9.4.3 Handling of missing values/censoring/discontinuations

Missing values will not be imputed.

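### Late mean changes in mUFC and blood pressure are in effect observed-case, so a trend after Week 22 can mix drug effect with a changing set of patients

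*SAP*

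**What the plan says.** SAP 7.3.2.2 states: "Descriptive statistics will be generated for the change from the respective baselines to different time points in mUFC", followed by ACTH, cortisol and a list of other hormones and electrolytes. SAP 7.3.2.3 says that the effect on metabolic abnormalities "will be assessed by descriptive statistics on the change from baseline in systolic blood pressure (SBP", then diastolic pressure, weight, BMI, lipids, QUICKI, HbA1c and FPG. Both add 95% confidence intervals. Neither gives an imputation rule, a planned model, a last-value summary or any other rule for patients who have left. The statistical modelling mentioned in 7.3.2.3 is optional and exploratory. Protocol 9.4.3, written for the primary variable, says "Missing values will not be imputed".

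The binary UFC endpoint is treated differently. SAP 7.3.2.1 says: "Early discontinued patients (including those discontinuing in the core phase) will be considered as non-responders for all time points after discontinuation". It makes the observed-only response rate a supportive analysis.

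On leaving, Protocol 5.5.11 lists among its stopping reasons "hypertension defined as office mean sitting systolic BP > 180 mmHg or mean sitting diastolic BP > 110 mmHg", if confirmed and persistent. The list is introduced by "Study treatment must be discontinued under the following circumstances and according to Investigator discretion". Protocol 3.5 and 5.5.7 provide for stopping or withdrawing patients with an unsatisfactory response or poor tolerance. Protocol 3.5 describes the extensions as open to responders with good tolerability.

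On numbers, the Amendment 9 rationale says that, of 19 patients, "10 patients are still ongoing as of 03 May 2018".

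**The concern.** SAP 3 says that the Final CSR concentrates on long-term efficacy and safety and rests its efficacy assessment on the secondary analyses. The HPA-axis and metabolic objectives are both kept for that report. A reader will look down the by-visit table and read a trend over several years.

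If patients with a poor UFC or blood pressure course are more likely to leave, the mean among those remaining can look better although no individual has improved. If patients leave because cortisol was lowered too far, the mUFC mean can look worse although no individual has lost control. The table as planned cannot separate either case from a real change over time.

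**Working it through.** **1. How each analysis treats a patient who has left.**

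| Analysis | Treatment of leavers |
|---|---|
| UFC response rate (SAP 7.3.2.1) | Early leavers count as non-responders at later time points; administrative exits and patients who did not enter the extension are left out; observed-only rate as support |
| Time to escape (SAP 7.3.2.4) | Kept until the last mUFC visit, then censored |
| Laboratory categories (SAP 7.5.2) | Shift tables to the most extreme and to the last value |
| Mean change in mUFC (SAP 7.3.2.2) | No rule |
| Mean change in SBP and DBP (SAP 7.3.2.3) | No rule; the vital-signs shift table in 7.5.3 uses notable values only |

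After stopping, a patient has one end-of-treatment visit and an end-of-study visit 28 days after the last dose (Protocol 6). Under SAP 8.3 the first is mapped to the next scheduled visit if it falls inside a window around that visit, and otherwise becomes unscheduled. The second is not mapped. At most one exit value therefore enters the by-visit means.

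**2. Which variables are tied to leaving.** Directly: blood pressure, UFC response (with no numeric limit), serum potassium (too high or too low) and low serum sodium. There is no stopping rule on weight, BMI, lipids, HbA1c, glucose, insulin or QUICKI, nor on ACTH, cortisol, 11-deoxycortisol, 11-deoxycorticosterone, aldosterone, renin, testosterone or estradiol.

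**3. Retention**, from the rationales of Amendments 6 to 9, out of 19:

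- completed the core: 17/19 = 89.5%
- entered extension-1: 16/19 = 84.2%
- November 2015: 12/19 = 63.2%
- June 2017: 11/19 = 57.9%
- May 2018: 10/19 = 52.6%, so 9/19 = 47.4% had left

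Counted from the 17 who completed Week 22, 7/17 = 41.2% had left by May 2018.

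**4. Possible size.** The plan states no figure for these summaries, so there is none to reproduce. The following simulations set the true mean change to zero and ask how far the mean of the remaining 10 of 19 moves.

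*(a) Exit correlated with the change.* Exit score = rho x change + sqrt(1 - rho^2) x noise, in SD units; the 10 lowest scores stay. The shift is 0 at rho 0, -0.18 SD at rho 0.25, -0.36 SD at rho 0.5 and -0.73 SD at rho 1, which is the bound.

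*(b) Of the 9 exits, j are the patients with the worst change and the rest are random.* Shift in mmHg = shift in SD units x assumed SD of the SBP change:

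| j | SD units | SD 10 | SD 15 | SD 20 |
|---|---|---|---|---|
| 1 | -0.10 | -1.0 | -1.5 | -2.0 |
| 3 | -0.27 | -2.7 | -4.0 | -5.4 |
| 5 | -0.42 | -4.2 | -6.3 | -8.4 |
| 9 | -0.73 | -7.3 | -10.9 | -14.5 |

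By symmetry, if the j exits were the patients with the largest reductions, the same figures apply with a plus sign.

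*(c) The written blood pressure rule alone*, taken as SBP above 180 or DBP above 110 at two consecutive visits. Assumed: baseline SBP mean 130 to 150, SD 12 to 18; baseline DBP mean 52 mmHg lower, with 0.6 times that SD; within-patient SD 8 and 6; zero-mean drift with SD 10 over 20 visits. The observed-case mean shifts by -0.05 to -1.66 mmHg, with 0.3% to 35% of patients removed.

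**5. What separates membership from trend.** Write M for a mean change from baseline, with the visit and the group in brackets:

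M(late; stayers) - M(Week 22; all) = [M(late; stayers) - M(Week 22; stayers)] + [M(Week 22; stayers) - M(Week 22; all)]

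The first bracket is a comparison within the same patients. The second is purely a change of membership. The planned tables print only the two terms on the left, so neither bracket can be read.

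**The case against.** The other side has a good deal to say.

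- The variables are not all alike. A reader might infer that the protocol removes patients on every variable in these two sections. Step 2 shows otherwise: for most of them bias would need an indirect link through UFC control or tolerability.
- The direction is not fixed. Potassium stopping is two-sided. Intolerance can reflect low cortisol: Protocol 5.5.4 covers signs of adrenal insufficiency with low UFC, and Protocol 3.5 reports symptoms of cortisol withdrawal in 4 patients. Losing such patients would worsen the mUFC mean.
- The blood pressure rule is a weak filter. It requires confirmation and persistence despite dose or medication changes, and leaves room for judgement. Step 4(c) puts it at under 2 mmHg.
- UFC is not unprotected, since the two response rates and the escape curve show the effect of attrition. Shift tables keep leavers for laboratory categories, and discontinuation reasons and individual listings are planned.
- Change is measured within patients, so losing patients with high baselines does not by itself move the mean.
- These are descriptive summaries in an exploratory single-arm study.

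All of this stands and narrows the point to mean change in mUFC and blood pressure. It does not remove it: none of these outputs shows how much of a late mean change in those two comes from a different set of patients.

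A reader might also infer that late means overstate the effect two to three times. Giving the 10 stayers -13 mmHg and the 9 leavers 0 to +5 yields (10 x -13 + 9 x 0)/19 = -6.8 and (10 x -13 + 9 x 5)/19 = -4.5, hence ratios of 1.9 and 2.9. That calculation assumes its answer. The nearest figure in the documents, -13.1 mmHg (Protocol 1.1.1.3), is a day-70 mean from the earlier cohort, not a value for stayers, and nothing is known of the leavers' changes.

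**Conclusion.** The point holds for mean change in mUFC, SBP and DBP after Week 22. The summaries are observed-case by silence rather than by statement, leaving is partly related to these outcomes, and 9 of 19 patients had left by May 2018. A late trend can therefore reflect who is still there as well as what the drug does.

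The presence, direction and size of any bias are unknown, because the documents do not give the reasons for the 9 exits. The figures in step 4 rest on assumed SDs and exit patterns. They show a range from nothing, through under 2 mmHg for the blood pressure rule alone, to -4.0 to -6.3 mmHg if 3 to 5 exits were outcome-driven at an SD of 15 mmHg. The documents do not support a claim that the late means are biased in the drug's favour, or that all listed variables are affected directly.

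**What to change.** In SAP 7.3.2.2 and 7.3.2.3, for at least mUFC, SBP and DBP and optionally the other variables, print at each visit after Week 22:

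1. n at that visit;
2. the current change from baseline;
3. beside it, the Week 22 change from baseline of the same patients observed at that visit.

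State that any long-term trend is read from items 2 and 3 together. The data exist: the core end-of-treatment visit carries these assessments, and SAP 8.3 maps it to Visit 12 for patients who continue.

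This comparison removes differences in membership. It does not remove selection on what happened after Week 22. For that reason a last on-treatment value for all SAS patients may be added as a supportive row, using values taken on drug only. The end-of-treatment visit of an early leaver is arranged after the decision to stop (Protocol 6) and may be off drug. Half-life is 3 to 5 hours (Protocol 1.1.1.4), and UFC was above ULN in 6 subjects measured at day 84, after stopping (Protocol 1.1.1.5). In the simulation of step 4(c) such a row lies +0.02 to +0.50 mmHg from the truth. It should not carry the long-term statement, because it mixes exits during titration with values after several years.

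The cost is one or two extra rows per table, with no new visits, imputation or data.
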